#### 9.2.1.2 Exclusion Criteria

Participants will not be included in the palovarotene-exposed cohort if:

- (1) Currently participating in any interventional clinical trial;
- (2) Palovarotene is contraindicated as per the locally approved label (except for pregnant participants who have previously received and discontinued palovarotene at any time during the pregnancy and who will be included for safety follow-up).

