**PAGE 40 OF 287** 

- a Follow-up Visits are recommended every 6 months, or as per local label.
- b If participant <18 years (or the legal age of consent in the jurisdiction in which the study is taking place), assent and parent or legally authorised representative consent will also be required.
- c This includes a general assessment, dermatologic, lymph nodes, HEENT, chest, cardiac, abdomen, limb/extremities, musculoskeletal, neurologic and other.
- d Not expected in the context of a telephone/video visit.
- e Collected for growing children. Assessment as per local label.
- f Linear height within 6 to 12 months prior to and at the Baseline Visit.
- g Vital signs to be collected are respiratory rate, blood pressure and heart rate.
- h Participants will be assessed for child-bearing status and pregnancy prevention measures. As per local label, pregnancy testing is carried out with a confirmation of absence of pregnancy monthly if the participant receives palovarotene and one month after stopping. These conditions also concern participants who are not currently sexually active unless the prescriber considers that there are compelling reasons to indicate that there is no risk of pregnancy.
- i This includes a period of two months prior to the signed informed consent date.
- i Not applicable for pregnant participants.
- k Spirometry obtains the lung function parameters of observed and % predicted FVC and FEV1 and the absolute and % predicted FEV1/FVC ratio. The DLCO test obtains observed and % predicted DLCO which provides information on the efficiency of gas transfer from alveolar air into the bloodstream.
- 1 This includes number of flare-ups over the past 12 months before the signed informed consent date.
- m Spinal health assessment to be performed using radiological imaging (e.g. CT, X-ray, scintigraphy, etc).
- n AE, SAE, Special Situation and AESI collection begins once the informed consent has been signed.
- o Paper-based patient-reported questionnaires.

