# 9.2.9 Treatment Discontinuation (Palovarotene)

Palovarotene treatment may be discontinued in the event of any AEs (see Section 11.1.1 for definition), SAEs (see Section 11.1.2 for definition), Special Situations (see Section 11.1.3 for definition), or AESIs (see Section 11.1.4 for definition) deemed by the investigator to warrant treatment discontinuation. In the event of pregnancy, palovarotene treatment must be discontinued (see Section 11.1.3.1).

Discontinuation of treatment due to AEs should be distinguished from discontinuation/withdrawal from the registry study due to participant/parent decision or end of follow-up.

If AEs or their sequelae (any AE, based on the investigator's opinion, not only those assessed as related) persist after the date of palovarotene discontinuation, the investigator must ensure that the participant receives appropriate medical follow-up and this should be properly documented in the participant's medical records.

All participants discontinuing palovarotene treatment will be followed up to 30 days after last palovarotene intake (unless consent is withdrawn).

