**PAGE 65 OF 287** 

#### Pregnancy

Confirmation of an absence of pregnancy will be included in the participant data listings using the Safety Exposed Population only.

Incidence of all pregnancies will be summarised for those exposed and unexposed to palovarotene in the Safety Exposed Population. For these analyses, the pregnancy will be considered as exposed to palovarotene if it occurs whilst the participant is using the medicinal product or within 2 days after stopping the product (based on the estimated date of conception).

For participants who become pregnant while enrolled in FOPal, whether exposed or not to palovarotene, pregnancy characteristics and outcomes, pregnancy-related AEs through the first year postpartum, and birth and developmental outcomes through the infant(s)' first year of life will be descriptively summarised by palovarotene exposure status (exposed and unexposed).

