### 11.1.3 Special Situations

A Special Situation is any incidence of drug exposure during pregnancy (i.e. drug exposure to a foetus in utero (whether the foetus is exposed via the mother taking the product)) or breastfeeding, overdose, underdose, off-label use, misuse, abuse, occupational exposure, medication errors/Intercepted medication error/Potential medication error, counterfeit/falsified medicinal product, unexpected therapeutic benefit, suspected transmission of an infectious agent via a medicinal product, drug interaction, drug dependence or lack of therapeutic effectiveness whilst using the medicinal product. A "Special Situation" should be collected by the investigator and reported to Ipsen whether or not these "Special Situations" are associated with an AE.

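### Pregnancy exposure is decided by conception date alone, so a pregnancy conceived off palovarotene and then dosed is tabulated as unexposed

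*Protocol*

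**What the plan says.** Section 9.7.3.4 (Pregnancy) treats a pregnancy as "exposed to palovarotene if it occurs whilst the participant is using the medicinal product or within 2 days after stopping the product", and adds that this is "based on the estimated date of conception". It has no clause for intake after conception.

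The status is used twice. Pregnancy incidence is reported as exposed or unexposed within the Safety Exposed Population. Pregnancy characteristics and outcomes, pregnancy-related adverse events, and birth and infant outcomes are then summarised by the same two groups.

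Other sections bear on it:
- Section 11.1.3 defines exposure during pregnancy as a Special Situation, meaning "drug exposure to a foetus in utero" through the mother's intake. It does not depend on when conception occurred.
- Section 9.2.1.2 lets in a pregnant participant who has "previously received and discontinued palovarotene at any time during the pregnancy", so dosing during a pregnancy is foreseen.
- Table 2, note h, provides for "confirmation of absence of pregnancy monthly if the participant receives palovarotene and one month after stopping".
- Section 9.3.2.9 collects palovarotene dose modifications, interruptions, and start and end dates.

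**The concern.** Harm to an embryo depends on whether drug is present during the pregnancy, and conception date is only a proxy for that. The proxy works when conception occurs on treatment. It fails when conception occurs off treatment and dosing starts or resumes before the pregnancy is known.

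Section 11.1.3.1 calls palovarotene highly teratogenic, and section 7.3.1 says no pregnancies were reported in development. Each pregnancy in the registry will therefore carry weight. A dosed pregnancy with an abnormal outcome, placed in the unexposed column, would make the exposed results look better and the background look worse.

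The unexposed column is also thinly supplied. Under section 9.7.1, everyone in the Safety Exposed Population has taken at least one dose. Under section 9.2.8, participants who stop for reasons other than safety or pregnancy are withdrawn, and section 9.2.9 limits follow-up after stopping to 30 days. So unexposed pregnancies in this population arise mainly before a first dose, during an interruption, or soon after stopping. The first two are where the rule can miss later dosing.

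**Working it through.** The plan has no numerical result to reproduce here. The check applies the section 9.7.3.4 rule to dosing histories and compares the result with actual intake during pregnancy.

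**Definitions.** Set conception at day 0. A dosing interval runs from day *s* (start) to day *e* (stop).
- Section 9.7.3.4 rule: exposed if *s* ≤ 0 ≤ *e* + 2 for some interval.
- In utero dosing (section 11.1.3 sense): some interval has *e* ≥ 0 and starts before the pregnancy ends.

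The histories are illustrative; the dates are assumptions.

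| History | Dosing interval(s) | Test of rule | Status under 9.7.3.4 | Dosed in utero? |
|---|---|---|---|---|
| A. Conceived on drug, dosing continues | −100 to 20 | −100 ≤ 0 ≤ 22, true | Exposed | Yes |
| B. Conceived 10 days before first dose | 10 to 35 | 10 ≤ 0, false | Unexposed | **Yes** |
| C. Conceived 10 days into an interruption, then restarted | −100 to −10; 5 to 30 | 0 ≤ −8, false; 5 ≤ 0, false | Unexposed | **Yes** |
| D. Conceived 2 days after stopping | −100 to −2 | 0 ≤ 0, true | Exposed | No later dose |
| E. Conceived 3 days after stopping | −100 to −3 | 0 ≤ −1, false | Unexposed | No later dose |
| F. Conceived 28 days after stopping | −100 to −28 | 0 ≤ −26, false | Unexposed | No later dose |

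B and C are the error: drug was taken during the pregnancy, yet the status is unexposed. A is handled correctly. D, E and F show where the 2-day limit falls and involve no later dosing.

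**Effect of one misplaced case.** Suppose correct classification gives *a* abnormal outcomes among *n* exposed pregnancies and *b* among *m* unexposed. Moving one dosed pregnancy with an abnormal outcome gives:
- exposed: *a*/*n* becomes (*a* − 1)/(*n* − 1), which is lower unless every exposed outcome is abnormal;
- unexposed: *b*/*m* becomes (*b* + 1)/(*m* + 1), which is higher unless every unexposed outcome is abnormal.

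Both shifts are largest when *n* and *m* are small, which is the expected situation.

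**After the change.** Adding intake from conception to the end of pregnancy turns B and C into exposed and leaves A, D, E and F as they are.

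**The case against.** The strongest reply is that the gap is narrow and the cases remain visible elsewhere. Pregnancy testing is scheduled at Baseline and monthly on treatment, child-bearing status is assessed before treatment (section 9.3.2.7), and an unexposed participant who becomes pregnant is withdrawn (section 9.2.8). In utero exposure is itself a Special Situation, listed and tabulated under section 9.7.3.2. All pregnancies are reported within 24 hours (section 11.2.2), and abnormal outcomes are SAEs (section 11.1.3.1). The pregnancy summaries are descriptive, and pregnancy is not among the outcomes compared between cohorts. This all stands as to frequency and detection. It does not correct the section 9.7.3.4 tables, where the same case would still be counted as unexposed.

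It can also be argued that the words on conception date qualify only the 2-day clause, so that any overlap of pregnancy and use counts as exposed. That reading is strained: the sentence places the pregnancy at a single point in time, on treatment or shortly after. If overlap is intended, the text should say so.

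Three stronger readings are tempting but not supported:
- **That any embryo dosed after conception is called unexposed.** History A shows otherwise.
- **That section 9.2.1.2 contradicts the rule.** It is an eligibility exception, and a woman who stops during pregnancy will usually have conceived on drug and so be classed as exposed.
- **That conceptions from day 3 to about a month after stopping are misclassified.** Most of that month does lie outside the 2-day window, but the one-month and 30-day periods concern pregnancy testing, adverse event collection and follow-up. They make no statement about how long drug persists. The protocol gives no elimination data, so it neither justifies nor refutes 2 days.

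**Conclusion.** The point holds in a limited form. Section 9.7.3.4 does not count intake after an off-drug conception, and this conflicts with the in utero definition in section 11.1.3. The affected pregnancies are those conceived before the first dose, or more than 2 days into an interruption, and then dosed before detection.

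They should be uncommon, and the documents give no conception or interruption rates from which to estimate how many. The importance rests on two assumptions: that few pregnancies will occur, which fits the absence of any in development and a minimum exposed target of 67 with about half paediatric, and that the exposed and unexposed outcome tables will be read side by side. Under those conditions one misplaced case can distort both columns. No error is shown in the 2-day window itself.

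**What to change.** In section 9.7.3.4, keep the present criterion and add an alternative. A pregnancy is exposed if conception occurs on treatment or within 2 days after stopping, **or** if any palovarotene dose is taken from the estimated conception date to the end of the pregnancy. Carry the same definition into the SAP.

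For every pregnancy, list the days from last dose to estimated conception and any dose taken after conception, so that a reader can see how each case was assigned. A sensitivity listing with a wider window after stopping is optional.

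The cost is one clause and one listing. Dose start and stop dates and interruptions are already collected under section 9.3.2.9, and the existing rule already needs an estimated conception date. No new data or change to treatment rules is involved. The change should be made before any pregnancy is tabulated.

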# Comparison of key safety outcomes between the Safety Exposed and the Safety Unexposed Populations

The key secondary endpoints that will be descriptively compared between exposed and unexposed participants with FOP in the FOPal registry, include: 1) Annualised frequency of flare-ups categorised by overall occurrence; 2) Annualised linear height velocity and height z-scores until skeletal maturity or final adult height is reached; knee height may also be evaluated depending on data availability, and 3) Annualised frequency and descriptive characteristics of bone fractures, categorised by overall occurrence and location.

The index date (Day 1) corresponds to the initial administration of marketed palovarotene for the exposed participants (naïve and non-naïve), and to the ICF signed date for unexposed participants.

Participants in the Safety Unexposed Population will be followed from their index date until data extraction at the end of FOPal registry, or until start date of palovarotene, or any investigational or commercialised FOP first treatment intake, whichever comes first.

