**PAGE 31 OF 287** 

FOP was consistent across adult ( $\geq$ 18 years) and paediatric ( $\geq$ 8/10 to <18 years) age subgroups except for epiphyses premature fusion. Some mucocutaneous effects such as decubitus ulcers had a higher incidence in adult participants, which was consistent with disease burden, increasing disability and prolonged exposure to corticosteroids.

Radiological vertebral fractures (PT: Spinal fracture) were identified as a risk associated with palovarotene based on retrospective analyses performed on WBCT data in participants with FOP in the Phase 3 (MOVE) study.

No pregnancies were reported during the clinical development programme.

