**PAGE 39 OF 287** 

 Table 2
 Schedule of Assessments: Exposed Naïve Participants

Assessment/Procedure	Baseline Visit	Follow-Up Visits (as per routine clinical practice[a])/ End of Study Visit
Clinic visit or telephone/video contact visit	X	X
Informed consent [b]	X	
Inclusion/exclusion criteria	X	
Baseline demographics	X	
Physical examination [c,d]	X	X
Medical or surgical history	X	
FOP history	X	
Growth status assessment (bone age, knee height and epiphyseal status) [d,e]	X	X
Tanner staging [d,e]	X	X
Linear height [f] and weight [d]	X	X
Vital signs [d,g]	X	X
Pregnancy testing [h]	X	X
Prior /concomitant medications [i]	X	X
Concomitant surgery and non-drug therapies	X	X
Prior use of palovarotene (investigational product)	X	
Palovarotene dose for chronic and flare-up treatment [j]	X	X
Spirometry and DLCO test [d,k]	X	X
CAJIS [d]	X	X
Movement mobility history (including flare-ups [1])	X	
Movement mobility changes (including flare-ups)	X	X
Spinal health assessment [m]	X	X
AEs, SAEs, Special Situations, and AESIs [n]	X	X
Participant Questionnaires:		
FOP-PFQ assessment [o]	X	X
PROMIS Global Health Scale [o]	X	X
FOP assistive devices assessment [o]	X	X

AE=Adverse Event; AESI=Adverse Event of Special Interest; CAJIS=Cumulative Analogue Joint Involvement Scale; CT= Computed Tomography; DLCO=Diffusion Capacity of the Lung for Carbon Monoxide; FEV1=Forced Expiratory Volume in one second; FOP=Fibrodysplasia Ossificans Progressiva; FOP-PFQ=FOP-Physical Function Questionnaire; FVC=Forced Vital Capacity; HEENT= head, eyes, ears, nose and throat; PI=Prescribing Information; PROMIS=Patient-Reported Outcomes Measurement Information System; SAE=Serious Adverse Event; SS=Special Situation.

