#### Spinal Health Assessment for Exposed Participants

The FOPal registry study will collect the outcome/results of radiological imaging and the type of imaging used to assess the participants' spinal health status in clinical practice, as recommended by the product label. The type of radiological imaging techniques for which outcomes/results will be collected include, but are not limited to, CT, X-ray and scintigraphy.

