#### *Fractures (including vertebral fractures)*

The FOPal registry study will collect the severity and descriptive details of any fractures (including vertebral fractures) in the SAE eCRF page from the signed informed consent date. For exposed non-naïve participants, any fractures that occurred between the first marketed palovarotene intake and the signed informed consent date will be recorded at the Baseline Visit using a different form. For unexposed participants, any fractures occurring within 12 months preceding the signed informed consent date and during the study will be recorded using the medical events of special interest eCRF pages.

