**PAGE 74 OF 287** 

# 11 MANAGEMENT AND REPORTING OF ADVERSE EVENTS, SERIOUS ADVERSE EVENTS, SPECIAL SITUATIONS AND ADVERSE EVENTS OF SPECIAL INTEREST FOR EXPOSED PARTICIPANTS

### 11.1 Definitions

### 11.1.1 Adverse Event

### **AE Definition**

An AE is any untoward medical occurrence in a patient/participant, administered a medicinal product (palovarotene) and which does not necessarily have a causal relationship with this treatment.

NOTE: An AE can therefore be any unfavourable and unintended sign (e.g. an abnormal laboratory finding), symptom, or disease temporally associated with the use of the medicinal product, whether or not related to the medicinal product.

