**PAGE 76 OF 287** 

Any radiological or clinical fracture, or PPC, must be reported as serious (seriousness criteria should be "important medical event" if no other seriousness criteria are present (e.g. hospitalisation)).

Is a suspected transmission of any infectious agent via an authorised medicinal product

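### The exposed-unexposed fracture comparison may not separate a drug effect from unequal spinal imaging, because imaging is recorded only for exposed participants and the compared fractures are not defined

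*Protocol*

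**What the plan says.** Fractures are one of three outcomes chosen for the between-cohort comparison. In Section 9.7.3.4 the compared quantity is "Annualised frequency and descriptive characteristics of bone fractures, categorised by overall occurrence and location". It is to be reported as estimates with 95% confidence intervals and without hypothesis testing, after inverse probability weighting on a propensity score.

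Imaging is handled differently in the two cohorts:

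- **Exposed.** Section 9.3.2.7 has an entry headed "Spinal Health Assessment for Exposed Participants", under which the registry collects imaging results on "spinal health status in clinical practice, as recommended by the product label". Table 2 schedules the item at baseline and follow-up for naïve participants. Table 3 schedules it at first marketed intake and follow-up for non-naïve participants. Section 9.7.3.5 lists the results for the Safety Exposed Population.
- **Unexposed.** Table 4 has no spinal imaging row, and neither do the visit lists in Sections 9.2.7.2 and 9.2.7.4. Under the fracture entry of Section 9.3.2.7, any fracture in the 12 months before consent and "during the study will be recorded using the medical events of special interest eCRF pages".

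Section 11, whose title restricts it to "ADVERSE EVENTS OF SPECIAL INTEREST FOR EXPOSED PARTICIPANTS", adds in 11.1.2: "Any radiological or clinical fracture, or PPC, must be reported as serious".

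Section 7.3.1 says that vertebral fractures were identified as a risk of palovarotene "based on retrospective analyses performed on WBCT data in participants with FOP".

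**The concern.** A comparison of event rates assumes that an event has a similar chance of being found in each cohort. Here one cohort has a label-prompted search of the spine with a place in the database for the result. The other has neither in the protocol. The protocol's own account of how vertebral fractures came to light, by re-reading CT scans, suggests that at least some are found by looking and not by symptoms.

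If such fractures count in the compared endpoint, more of them will tend to be found in the exposed even when the true rates are equal. This matters because fracture is an identified risk and this is the protocol's only planned between-cohort contrast on it. A weighted estimate with an interval will be read as a safety contrast, whether or not a test is attached. The opposite misreading is also possible: a real excess could be dismissed as detection, and without imaging data from the unexposed nobody could tell which reading is right.

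**Working it through.** **Step 1: do the compared fractures include imaging-found ones?** The protocol does not settle this.

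- The secondary objectives (Section 8.2.2) name bone fractures and vertebral fractures side by side, as if distinct.
- Section 9.3.1.2 has one endpoint on any fractures and another on bone fractures. Section 9.7.3.4 compares the second.
- The fracture analysis in the same Section 9.7.3.4 is headed as including vertebral fractures.
- No passage defines bone fractures or excludes vertebral or imaging-only events.

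**Step 2: can the planned adjustment deal with it?** The named propensity covariates are age, gender, time since last flare-up and total CAJIS score, all at the index date. Weighting balances baseline characteristics. It does not change the chance that a later fracture is seen. More covariates are allowed, but use of spinal imaging could not serve, since it is not collected in the unexposed.

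**Step 3: does the protocol acknowledge it?** Section 9.9 mentions missing data and variation between sites, not detection that differs by exposure. The ENCePP checklist (Appendix 1) marks item 7.3, on information bias, as not applicable.

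**Step 4: how large could it be?** The protocol gives no fracture rate and no imaging-only share, so there is no figure to reproduce. Every input here is an assumption. Let the true rates be equal, *s* the share of fractures visible only on imaging, and *dE* and *dU* the shares of those detected in exposed and unexposed. Then

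apparent rate ratio = (1 − s + s·dE) / (1 − s + s·dU).

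With dE = 1 this becomes 1 / (1 − s(1 − dU)):

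| s | dU = 0.5 | dU = 0 |
|---|---|---|
| 0 | 1.00 | 1.00 |
| 0.10 | 1/0.95 = 1.05 | 1/0.90 = 1.11 |
| 0.25 | 1/0.875 = 1.14 | 1/0.75 = 1.33 |
| 0.50 | 1/0.75 = 1.33 | 1/0.50 = 2.00 |

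The dU = 0 column is an upper bound. If detection is incomplete in the exposed as well, say dE = 0.8 and dU = 0.2, the ratio at s = 0.50 is 0.9/0.6 = 1.50, and at s = 0.25 it is 0.95/0.80 = 1.19. With dE = dU, or with s = 0, it is 1.00.

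**Step 5: how does this compare with precision?** Take the minimum cohort sizes of 67 and 33 (Section 9.7.2) and assume 0.1 fractures per person-year, Poisson counts, equal follow-up and no weighting.

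- Two years: 67 × 2 × 0.1 = 13.4 and 33 × 2 × 0.1 = 6.6 events. SE of the log rate ratio = √(1/13.4 + 1/6.6) = 0.476. The 95% interval is the estimate divided and multiplied by exp(1.96 × 0.476) = 2.54.
- Five years: 33.5 and 16.5 events, factor 1.80.

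A bias of 1.05 to 1.14 is small against such intervals. A bias near 2 is not. Longer follow-up narrows the interval but leaves the bias unchanged.

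**The case against.** The strongest reply has five parts.

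1. **Unexposed fractures are collected.** Any fracture is recorded in both cohorts, so a fracture found on routine imaging of an unexposed participant is captured. This stands. Detection is unequal in degree, not absent on one side. A reader might infer that the comparison is nothing but a detection artefact, or that the exposed rate is bound to be higher. The documents do not support that: clinically apparent fractures are captured in both cohorts, and the imaging-only share is not given.
2. **Imaging is not mandated in the exposed either** (Section 9.2.6), and retrospective spinal data for non-naïve participants are taken only at first marketed intake (Table 3). This also stands, so full detection in the exposed is an assumption. The seriousness rule in Section 11.1.2 governs how a fracture is classed and does not widen which fractures are collected.
3. **Bone fractures may exclude vertebral ones.** That is a fair reading of Section 8.2.2, and on it spinal imaging would hardly affect the contrast. The protocol does not say so, and an undefined endpoint in a key comparison needs settling in either case.
4. **Categorising by location already helps.** Partly: a spinal category could be read apart. It would not distinguish symptomatic from imaging-only fractures, and the overall rate would still pool them.
5. **The comparison is secondary and descriptive, and the SAP can refine it.** The descriptive status lowers the severity. But an SAP cannot recover data that were never collected, and without a record of who was imaged in the unexposed cohort no imaged-only analysis is possible.

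**Conclusion.** The point holds in a conditional form. Spinal imaging is recorded only in the cohort whose imaging the label prompts. If vertebral or imaging-only fractures fall within the compared bone fractures, the contrast cannot separate a drug effect from differential imaging, and the likely direction is towards more fractures in the exposed. The planned weighting does not address this, and the limitations section is silent on it.

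The size cannot be derived from the documents. Under the stated assumptions it runs from negligible (1.05) to a doubling (2.00) for imaging-only shares of 10% to 50%. The upper end requires that no imaging-only fracture is detected in the unexposed. The conclusion also assumes that routine spinal imaging is less frequent in the unexposed. The protocol suggests this but does not state it.

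This should be fixed. It does not undermine the primary safety objective, which concerns exposed participants only.

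**What to change.** **Section 9.7.3.4.** State whether vertebral and radiological fractures belong to the compared endpoint. Make clinically presenting fractures the main contrast. Show vertebral and imaging-only fractures separately by cohort, so that the identified risk stays visible. Add a sensitivity comparison limited to participants with spinal imaging. Read it with care, since unexposed participants who are imaged may have been imaged because of symptoms.

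**Data collection.** Add a mode-of-detection field (symptoms or imaging) to all three fracture forms: the SAE page, the retrospective form for non-naïve participants and the medical-events page for the unexposed. The retrospective form matters because follow-up in the comparison starts at first marketed intake. Add a row to Table 4 for routine spinal imaging: done or not, date and result, if available.

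**Section 9.9.** State that fracture detection may differ by exposure, and bring item 7.3 of the ENCePP checklist into line.

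**Cost.** Wording, a few eCRF fields and no added imaging, which fits the observational design. Data collection was planned to start in Q4 2024, so records already entered would need back-filling where sources allow, and delay loses information. The main contrast would have fewer events. If half of all fractures were imaging-only, the two-year example would fall from 13.4 and 6.6 events to 6.7 and 3.3, and the interval factor would rise from 2.54 to exp(1.96 × √(1/6.7 + 1/3.3)) = 3.74.

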# 9.2.8 Registry Study Discontinuation/Withdrawal

The participant can withdraw (or be withdrawn if the subject is a child upon legal representative's decision) from the FOPal registry study at any time. The date and primary reason for withdrawal should be recorded in the eCRF as well as whether the participant stopped or not palovarotene for exposed participants.

Should the participant withdraw from the study, no further data will be collected, nevertheless, data collected up to the time of the withdrawal will be kept for analysis, safety and integrity of study results.

The participant will be withdrawn from the FOPal registry study if:

- The participant enrols in any interventional clinical trial for FOP, or,
- For exposed participants: the participant is no longer receiving palovarotene (except if palovarotene is discontinued due to a safety concern or pregnancy, in such cases the participant will be monitored for safety, see Section 11.4 for follow-up of AEs and Section 11.1.3.1 for follow-up of pregnancies).
- For unexposed participants: the participant becomes pregnant or starts a treatment for FOP other than palovarotene. In case the participant starts palovarotene, they should have the option to remain in the registry. Previously unexposed participants starting palovarotene and remaining in the registry will follow the exposed naïve participants schedule (Table 2) from the first marketed palovarotene intake.

Investigators, participants or/and parents may decide to stop the participation in the FOPal registry study at any time without consequences on the normal participant clinical care.

PAGE 50 OF 287

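### The end-of-follow-up rule for unexposed participants omits study exit, so unobserved time could enter the control denominator of the annualised rates

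*Protocol*

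**What the plan says.** The part of section 9.7.3.4 that compares key safety outcomes between the exposed and unexposed populations sets the control follow-up: "Participants in the Safety Unexposed Population will be followed from their index date until data extraction at the end of FOPal registry". The same sentence allows two earlier end dates and takes whichever of the dates comes first. That makes three possible end dates: data extraction, start of palovarotene, and first intake of another FOP treatment, whether investigational or marketed.

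Section 9.2.8 sets out when observation actually stops:

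- On withdrawal: "Should the participant withdraw from the study, no further data will be collected". Data gathered before then are kept.
- Voluntary exit: "Investigators, participants or/and parents may decide to stop the participation in the FOPal registry study at any time".
- Required exit for any participant: "The participant enrols in any interventional clinical trial for FOP".
- Required exit for unexposed participants: "the participant becomes pregnant or starts a treatment for FOP other than palovarotene".

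Two of the three compared outcomes are rates per year. One is "Annualised frequency of flare-ups categorised by overall occurrence"; the other is the annualised frequency of bone fractures. The protocol does not define the time denominator for either. The comparison section also gives no end of follow-up for exposed participants.

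**The concern.** The phrase about whichever date comes first makes the list read as closed. Withdrawal, pregnancy, death and loss to follow-up are not on it, so follow-up as defined can run past the point where section 9.2.8 says that observation ends. The resulting interval is the only control follow-up time that the protocol supplies for these rates. If it serves as time at risk, a control who leaves early keeps contributing years in which no event could have been recorded.

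The direction is predictable: the control rate falls and the exposed/unexposed ratio rises, so palovarotene would look worse on fractures and possibly on flare-ups. Fractures are an adverse event of special interest (section 9.3.2.5), and section 7.3.1 names vertebral fractures as a risk identified in the phase III study. The fracture comparison is therefore one that readers of the final report will look at closely.

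**Working it through.** The protocol gives no rate, person-time or attrition figure, so there is nothing of its own to reproduce. The check has two parts.

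**Which exits the list already covers**

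| Exit under 9.2.8 or in general | On the 9.7.3.4 list? |
|---|---|
| Starts palovarotene | Yes |
| Starts another FOP treatment | Yes |
| Enrols in an interventional FOP trial | Largely: cut at first investigational intake. Only the time before intake, or an arm without such intake, is uncovered |
| Pregnancy | No |
| Voluntary withdrawal | No |
| Death | No |
| Loss to follow-up | No |

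**Illustrative size**

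Inputs from the protocol: at least 33 unexposed participants (section 9.7.2); enrolment over at most 10 years and a registry of up to 11 years (section 9.2.4).

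Assumptions, none of them in the protocol:
- Enrolment is uniform, so the time T from index date to data extraction is uniform on 1 to 11 years, with mean 6.0.
- Exits of the uncovered kinds occur at a constant hazard w, independent of events.
- The event rate is constant.
- The exposed denominator is correct.

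The time counted under the list as written is 6.0 years per control, or 33 × 6.0 = 198 person-years. The mean observed time is the average of (1 − exp(−wT))/w over T, which is

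(1/w) × [1 − (exp(−w) − exp(−11w)) / (10w)].

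At w = 0.05: exp(−0.05) = 0.9512 and exp(−0.55) = 0.5769. The difference is 0.3743, and divided by 0.5 it is 0.7486. Then (1 − 0.7486)/0.05 = 5.03 years. The control rate is multiplied by 5.03/6.0 = 0.838, and the rate ratio by 1/0.838 = 1.19.

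| Assumed w per year | Mean observed years | Observed person-years (33 controls) | Control rate multiplied by | Rate ratio multiplied by |
|---|---|---|---|---|
| 0.03 | 5.39 | 178 | 0.898 | 1.11 |
| 0.05 | 5.03 | 166 | 0.838 | 1.19 |
| 0.10 | 4.28 | 141 | 0.713 | 1.40 |
| 0.15 | 3.69 | 122 | 0.616 | 1.62 |

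If the same percentages are read as annual probabilities, w = −ln(1 − p). The control multipliers become 0.896, 0.834, 0.702 and 0.595, and the ratio multipliers 1.12, 1.20, 1.42 and 1.68. Either reading gives a range of about 1.1 to 1.7. If follow-up ends at exit, both multipliers are 1.00.

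**Which outcomes are touched**

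- Fractures: yes, since a rate per year needs a time at risk.
- Flare-ups: less certainly. Sections 9.3.2.8 and 9.7.3.4 collect and present them as the number since the last visit, so each count already belongs to an interval closed by a visit.
- Height velocity and z-scores: no. They are derived from dated measurements (section 9.7.3.4, Growth Status).

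**The case against.** The strongest reply is that the protocol never says that time runs to data extraction for someone who has left. Sections 9.7.3.4 and 9.2.8 can be read together to mean that a withdrawn participant is no longer followed. Section 9.7.3 leaves technical detail to a separate statistical analysis plan, which is not at hand, and a careful analyst would stop at last contact. This stands to the extent that the bias is conditional. It does not remove the defect. The protocol does not merely leave the end date open; it fixes it by a list that omits exit. An analysis plan that follows the list inherits the error, and one that departs from it contradicts the protocol.

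Three stronger readings are tempting, and the protocol does not support them:

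- **That trial entry is a main route for unobserved time.** The list already ends follow-up at first investigational intake, so only the gaps noted in the table remain.
- **That the error falls on controls alone, because exposed collection ends 30 days after last intake.** That rule governs adverse event collection and follow-up after stopping the drug (sections 9.2.9, 9.3.2.5 and 11.2.1). The comparison section sets no end date for exposed participants. Section 9.2.8 allows for someone who withdraws while still taking palovarotene, so the same gap could arise there.
- **That the control rate is certainly biased by a known amount.** No attrition rate is stated, and only exits outside the existing list count.

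It is also fair to say that the comparison is secondary and descriptive, without hypothesis testing (sections 9.7.3.1 and 9.7.3.4), and that the primary safety objective in exposed participants is untouched.

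**Conclusion.** The point holds as an inconsistency between two rules. The end-of-follow-up list in section 9.7.3.4 omits withdrawal (including required withdrawal at pregnancy), death and loss to follow-up, while section 9.2.8 ends data collection at withdrawal. If the listed interval is used as time at risk, the control fracture rate would be understated, and less certainly the control flare-up rate.

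Under the assumptions stated, uncovered exit rates of 3% to 15% per year would inflate the exposed/unexposed ratio by about 1.1 to 1.7. The true size is unknown, and it is zero if follow-up is cut at exit. Severity is moderate: the analysis is descriptive, but it reports estimates with 95% confidence intervals, and a wrong denominator distorts both.

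**What to change.** In section 9.7.3.4:

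1. End unexposed follow-up at the earliest of the last contact at which the outcome was ascertained, withdrawal for any reason (including pregnancy and trial enrolment), death, start of palovarotene or another FOP treatment, and data extraction.
2. Define annualised frequency as events divided by that observed time.
3. State the matching end of follow-up for exposed participants, so that both groups' denominators follow the same principle.

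This takes a few sentences and changes no visit, assessment or clinical rule. Withdrawal dates are already to be recorded in the eCRF (section 9.2.8). The date of death is specified only for exposed participants (section 9.3.2.5), so the sponsor should check that it is also captured for the unexposed.
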